7.0 TRIAL TREATMENTS

7.1 Description of investigational medicinal product(s)

The only Investigational Medicinal Product (IMP) used in the Next Generation ST study is capecitabine. This is a low intervention clinical study and the IMP used is standard for patients with rectal cancer.

7.1.1. Dose and administration

There is no international standard dosing for the combination of capecitabine with long course radiotherapy. The dose chosen in Next Generation ST is based on the STAR TREC study where patients received 825mg/m² bd five days per week.

A phenotypic or genotypic DPYD deficiency test is recommended prior to starting treatment to identify patients likely to develop severe capecitabine-related toxicities due to reduced catabolism/increased exposure. The reported DPYD result should be recorded in the CRF and will define subsequent patient management:

- Complete DPYD deficiency: Patient cannot be included in the study.
- Partial DPYD deficiency: Capecitabine starting dose to be reduced as per local guidelines

The following criteria must be met prior commencing treatment with capecitabine:

- Estimated creatinine clearance ≥ 50 ml/min
- Absolute neutrophil count $\geq 1.5 \times 10^9/L$
- Platelets $\geq 100 \times 10^9/L$
- Serum transaminase $\leq 3 \times$ Upper Limit Normal/L (ULN)
- Bilirubin $\leq 1.5 \times$ ULN

Capecitabine should be taken on the days of radiotherapy only (normally Monday-Friday). If radiotherapy is not given (e.g. due to bank holiday or machine breakdown, etc.) then capecitabine should not be taken. Capecitabine treatment can begin on any day of the week; however, **there is normally no capecitabine treatment on Saturday or Sunday**, unless radiotherapy is given on one of these days.

Patients are asked to swallow whole capecitabine tablets with a glass of water twice daily within 30 minutes after the ingestion of food, commencing the morning of the first dose of radiotherapy treatment. Tablets should not be crushed or cut.

It is recommended that patients keep a diary of the number of capecitabine tablets taken to assist site research staff in recording dose delivered.

7.1.2 Packaging, labelling, and handling of investigational medicinal products

Trial supplies of capecitabine for the entire treatment period will be prescribed and collected at the pharmacy during the study period. The costs for the drugs will be covered through the national drug insurance, and no drug costs will be reimbursed.

The full 5-week course of capecitabine can be dispensed at the start of treatment.

If a dose reduction is required before the end of the 5 weeks course due to toxicities, all remaining capecitabine tablets should be returned, patient weight re-measured and amended dose details in the dispensing label.

Capecitabine will be in commercial stock in standard packaging.

7.1.3 Drug accountability and treatment compliance

As this is a low- intervention clinical study we will not perform an extensive traceability rather, the responsible physician and nurse that have prescribed the chemotherapy will keep track of compliance and document if patients miss/skip a dose.

7.2 Auxiliary medicinal products

No auxiliary medicinal products are planned within the study.

7.3 Concomitant treatment of radiotherapy

7.3.1 Purpose and scope of radiotherapy guideline

This document is based on the previous radiotherapy guidelines from the STAR-TREC trial (EudraCT no 2016-000862-49)(35). The STAR-TREC study introduced the concept of mesorectal treatment planning in early rectal cancer with reduced target volumes compared to previous standard in rectal cancer irradiation. The aim of this document is to ensure uniform delivery of radiotherapy and the collection of high-quality data for study analysis.

7.3.2 Radiotherapy treatment planning

The use of Computed Tomography (CT) scan for treatment planning is considered standard practice and is a mandatory requirement. The scan limits are the superior aspect of L5 to 4 cm below the anal verge. The recommended slice thickness is 2-3 mm, but a slice thickness of up to 5 mm is accepted. The use of intravenous contrast is optional and should align with local centre policy. Magnetic Resonance Imaging (MRI) is strongly recommended for guidance in target definition.

7.3.3 Patient position and immobilisation

Patient set-up follows local routines. The supine position is recommended. If the prone position is used; belly board may be used but is not mandatory. This manual comprises no bladder or bowel protocol. Local routines should be followed, but a general recommendation is that the bladder should be comfortably filled and the rectum as empty as possible.

7.3.4 Definition of treatment volumes

All treatment volumes should be named according to current guidelines from the Radiation Safety Authority(43).

7.3.5 Gross tumour volume (GTV)

Gross tumour volume (GTV) is named GTVT_50. All macroscopic tumour is delineated on each slice. Only involved areas of the rectal wall are included. Rectal faecal contents are not to be include in the GTV.

7.3.6 Clinical target volume (CTV)

Clinical target volume (CTV) is named CTVT_50.

7.3.6.1 Superior limit

Is defined as the S2/S3 interspace. A minimum of 2 cm is required from the superior limit of the GTV to the CTV. If the tumour is localized in the upper rectum, CTV may be extended above S2/S3 interspace to achieve the 2 cm margin.

7.3.6.2 Inferior limit

Is defined as 2 cm inferior of the GTV. An exception is if the tumour is localized in the lower rectum and the CTV margin extends into the anal canal. A maximum of 1 cm of the anal canal should be included in CTV.

7.3.6.3 Anterior limit

The mesorectal fascia is contoured. If the mesorectal fascia disappears anteriorly, the anterior border is the anterior rectal wall. For cranial slices with no visible rectum, the anterior border is the defined by the contour used for the last carinal slice with visible rectum.

7.3.6.4 Posterior limit

Is defined as the anterior margin of the sacrum or coccyx, or the inner border of the puborectalis muscle in caudal slices.

7.3.6.5 Lateral limits

The mesorectal fascia is contoured. In the most cranial (high pelvis) and caudal slices (low pelvis) mesorectal fascia is not present. In high pelvis, the lateral border comprises the inner border of the piriformis muscle. In low pelvis, the lateral border comprises the inner border of

7.3.7 Planning target volume (PTV)

Planning target volume (PTV) is named PTVT_50. PTV margins will depend on local technique, image guidance schedule, and treatment setup procedure and uncertainties. If Cone Beam Computed Tomography (CBCT) is used for on-line imaging, the PTV margins may be reduced to 6-8 mm. If 2D kV (two-dimensional kilo voltage) imaging is used an anisotropic PTV margin is recommended: 10 mm margin in all directions except anteriorly where a 15 mm margin is recommended.

7.3.8 Organs at risk (OAR)

The following organs at risk (OAR) must always be delineated:

- Urinary bladder (Bladder)outer contour of the bladder as it appears on planning CT. The structure should be named Bladder according to established nomenclature.
- Bowel bag (BowelBag): The bowel bag is contoured superiorly from 1.5 cm above the most superior part of the PTV. Anteriorly to the inside of the abdominal wall.

Laterally, it is delineated from bowel edge to bowel edge. The posterior limit is the most posterior bowel edge. The most inferior limit includes the most inferior bowel that is not rectum or rectosigmoid junction.

- Bowel (Bowel): Individual bowel loops, excluding the rectum, is delineated within the bowel bag as defined above.
- Left and right femoral heads (FemoralHead_L; FemoralHead_R): Contoured to the most inferior extent including the lesser trochanter.

7.3.9 Dose and volume guidelines

Radiation therapy should be delivered with photon energies ≥ 6 MV using a linear accelerator. Volumetric modulated arc therapy (VMAT) is strongly. All fields must be treated during each treatment sessions.

A total dose of 50 Gy in 25 daily fractions over a total time of 5 weeks should be delivered, treating 5 days per week, 1 fraction per day using 2.0 Gy per fraction. This is combined with Capecitabine 825 mg/m² twice daily on radiotherapy treatment days.

7.3.10 Dose-volume objectives and constraints

The isocentric treatment plan is usually specified to receive 100% with the 95% isodose line encompassing the PTV and no more than +5 % and -5% inhomogeneity within the target volume. If OAR doses can be limited even further for the individual patient, without compromising target coverage, this should be attempted.

Priority	Structure	Dose-volume objectives
1	GTVT_50	D99% \geq 99%
1	CTVT_50	D99% \geq 98 % Dmean \geq 100 %
1	PTVT_50	D2% \leq 105 % D98% \geq 95 %
2	Body	D2% \leq 105 %
3	BowelBag	V20Gy < 180 cm ³ V30Gy < 130 cm ³ V45Gy < 90 cm ³
3	Bowel	V20Gy < 120 cm ³ V30Gy < 90 cm ³ V45Gy < 60 cm ³
3	Bladder	V35Gy < 22% V50Gy < 7%
R*	FemoralHead_L FemoralHead_R	V25Gy <15%

*Report value

7.3.11 Treatment verification

Generally, on-treatment imaging frequency should align with local policy. However, daily on-line imaging is highly recommended since reduced margins are used in mesorectal irradiation. If daily on-line imaging with CBCT is used, smaller PTV (6-8 mm) margins may be used.

7.3.12 Radiotherapy Quality Assurance (RTQA)

7.3.12.1 Pre-trial QA

Facility Questionnaire (FQ): general and trial specific questions on equipment, software and techniques to be used for the trial.

Benchmark Outlining and Planning Cases: Each study centre will need to submit a benchmark delineation case outlined by clinical oncologist involved in the study. Additionally, a benchmark planning case will need to be planned and submitted with a plan assessment form (PAF).

7.3.12.2 On-trial QA

Radiotherapy related data should be collected and reported by each centre for every patient and transferred to the QA centre at Sahlgrenska University Hospital within 2 months after finalizing radiotherapy. The data transfer is handled through the Skandionkliniken Sharefile service (<https://skandionibasa.sharefile.eu/home/shared>)

A folder named NGST_XX_YYYY, where XX is the number of the study site and YYY is the patient study number, should be created and include anonymized DICOM files for planning CT images, structure set (RS), registered images, treatment plan (RP) and dose (RD). Notify the RT-QA office that patient data has been uploaded by sending an e-mail to the study specific e-mail address: [contact]

A safety assessment will be performed after the first 10 RT plans to confirm adherence to the protocol regarding target delineation and dose planning.

7.4 Surgery

If the patient does not achieve complete response after the second evaluation after neoadjuvant treatment surgery will be recommended. Any deviation from this will be considered a protocol violation and must be registered. It is important that the patient understand that there is an increased risk of tumour progression if surgery is not performed at this stage.

The preoperative and perioperative treatment regarding anaesthesia and antibiotics and all other details must follow local guidelines.

All patients should be given pre-operative prophylactic antibiotics and antithrombotic medication such as low molecular heparin before the start of the operation. The type of antithrombotic medication should be registered in the eCRF. Any bowel preparation performed is according to local/regional/national routine. For the purpose of this study TME surgery is defined as previously published (44). No distinction is made between different surgical approaches. Laparoscopic, robot assisted laparoscopy, or open surgery can all be used and the choice is at the discretion of the surgeon.

7.5 Treatment after trial end

No specific treatment will be administered after the study.

8 METHODS FOR MEASUREMENT OF ENDPOINTS FOR CLINICAL EFFICACY AND SAFETY

8.1 Methods for measurement of endpoints for clinical efficiency

8.1.1 Primary endpoint

Primary variable: clinical complete response rate. Measured as the ratio of patients with a non-operative approach at onset that after evaluation by a combination of MRI, clinical and endoscopic examination have a clinical complete response at 1 year.

Definition of clinical complete response (cCR)

1. No suspicious metastatic lymph nodes or evidence of remaining tumour on MRI. In a majority a complete response on MRI will be seen as areas of homogeneous fibrosis. Absence of any remaining pathological tissue is seen in a minority of cases.
2. Endoscopic examination with white light. Presence of light/white mucosa or scar, telangiectasia. Presence of fibrosis and oedema.
3. No palpable tumour on clinical examination if the tumour was palpable initially.

Definition of near clinical complete response – possible to re-examine again after four weeks

1. The majority of the tumour is converted to fibrosis with homogeneous low signal intensity on T2-weighted images with minor areas of impeded diffusion on high b-value DWI.
2. Using white light endoscopy with phosphate enema (or comparable) bowel preparation any one of the following are encountered:
 - a. Residual mucosal irregularity
 - b. Residual flat ulcer
 - c. Submucosal irregularity or swelling

8.1.2 Secondary endpoints

Secondary outcome	Variable	Summary measure	Time point^o
Local recurrence	Registration in CRF	Proportion	3 years
Local regrowth	Registration in CRF	Proportion of patients that have achieved clinical complete response	1, 2 and 3 years
Surgical morbidity measured as Comprehensive Complications index^o	All complications registered according to Clavien-Dindo	Median value	90 days postoperatively in cases where surgery is necessary
Organ preservation rate at 3 years	Registration in CRF	Proportion	Patients with remaining rectum without deviating stoma at three years. Regardless of function.

Clinical complete response rate	Registration in CRF	Proportion	1 and 2- and 3-years follow-up after inclusion
R0 rate among operated patients	Registration in CRF	Proportion among operated patients	1 and 3 years after inclusion, both patients with initial organ preservation and TME resection surgery
Metastases	Registration in CRF	Proportion as well as subgroup specification of location	1 and 3 years after inclusion
Total length of hospital stay	Total number of days including readmissions	Median and range	Within 365 days after diagnosis
Quality of life	Measured in QoL questionnaire	Value baseline vs follow-up. Likert scale with dichotomization	Baseline, post treatment, at surgery if applicable and at one, two and three years
Urinary function	Measured in QoL questionnaire focus on incontinence, emptying difficulties and urgency	Value baseline vs follow-up and comparing groups	Baseline, post treatment, at surgery if applicable and at one, two and three years
Sexual function	Measured in QoL questionnaire, focus on both function and quality	Value baseline vs follow-up and comparing groups	Baseline, post treatment, at surgery if applicable and at one, two and three years
Bowel and stoma function	Measured in QoL questionnaire, major LARS	Value follow-up comparing groups	Baseline, post treatment, at surgery if applicable and at one, two and three years
Patients with a stoma	Measured as number of patients with a stoma/total number of patients	Proportion	One, two, three years
Health economic analysis	EQ5D as well as cost evaluation from both societal and health care sector perspective. Will include number of days on sick leave.		3 years after diagnosis
Mortality	Registration in CRF	Proportion	3 and 5 years after diagnosis
Patient satisfaction	Decision regret form		3 years after inclusion
5- year overall survival	Registration in CRF	Proportion	5 years after inclusion

° *Comprehensive Complications index* (45)

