Primary endpoint:	Clinical complete response rate evaluated by MRI and endoscopy at one year (i.e. patients that have not undergone surgery)
Secondary endpoint:	
 • Oncologic: 
 ○ Clinical complete response rate without surgical intervention at three years ○ Local recurrence at three years ○ Mortality at three years ○ Overall survival at three years • Surgical 
 ○ Surgical morbidity measured as Comprehensive Complications index at 90 days after surgery (if performed) ○ Total length of hospital stay during the first year ○ Outcome after surgery (Histopathological assessment of the resected rectal specimen to report (a) Presence of clear margins (>1mm from excision border to tumour edge), (b) TNM staging.) • Patient reported outcomes (all measured Baseline, post treatment, at surgery if applicable and at one, two and three years) 
 ○ Quality of life ○ Urinary function ○ Sexual function ○ Bowel and stoma function 
Health economic analysis at three years

Trial design:	
National, multi-centre, open-label, prospective trial.
 
Patients will choose possible organ preservation or standard surgery.
 
Those who prefer possible organ preservation will be offered treatment according to the experimental arm of the STAR TREC trial: mesorectal Chemoradiotherapy (CRT).
 
Those who prefer standard surgery or have no preference will undergo standard Total Mesorectal Excision (TME) surgery without neoadjuvant radiotherapy treatment.

Trial population:	Subjects referred to either a colorectal surgeon or the colorectal cancer multidisciplinary team (MDT) with suspected early stage rectal cancer (T1-T3bNx/N0). Diagnosis must be confirmed with a biopsy prior to study entry.
Number of subjects:	Due to the study design the number of patients to be included has not been fixed, but it is estimated to be at least 60-80 patients during the period until STAR-TREC data will be available
Inclusion criteria:	
 • Biopsy proven adenocarcinoma of the rectum < 12 cm • Magnetic Resonance Imaging (MRI)-staged TT1-3b, N0, MX/M0 rectal tumour • MDT determines that the following treatment options are all

	
reasonable and feasible: TME surgery or CRT
 
 • Eastern Cooperative Oncology Group (ECOG) performance status 0-1 • Willing and able to consent

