beam radiotherapy (9 Gy \times 5) or brachy radiotherapy (90Gy/3 fractions). They found that 64% of patients with external beam radiotherapy achieved a clinical complete response, compared to 92% after brachy radiotherapy. The 5-year local regrowth was 39% vs 17%, and some patients had their local regrowth after 3 years, indicating that long-term follow-up may be necessary. There are indications that patients that undergo brachy radiotherapy and then have incomplete response have very poor bowel function suggesting that studies are required to ascertain that patients receive correct information for shared decision making (38).

In summary there seems to be sufficient evidence that some patients will achieve clinical complete response after chemoradiotherapy with a long-term positive oncologic outcome (25), but long-term morbidity is not sufficiently described to date. This treatment will increase the risk for postoperative complications and increased risk for affected bowel function after both local excision and TME-surgery. Local excision may not always be adequate to treat insufficient response to chemoradiotherapy. Presently in Sweden there are no available treatment options apart from radical surgery (as recommended in the Swedish National Treatment Guidelines for Colorectal cancer) for patients with early rectal cancer while waiting for the long-term results from the STAR-TREC trial. The CORRECT trial has commenced in Stockholm and Uppsala in 2025 offering treatment options with contact therapy (brachy radiotherapy).

2.4 Rationale and design of the Next generation study awaiting the results from the STAR-TREC study

In light of the promising results from smaller studies, and the positive experience from treatments centres within the STAR-TREC trial this study aims to offer a treatment option to patients with early rectal cancer in a prospective phase II study to enable evaluation of results, and to enable comparisons with results from present and future studies until results from the STAR-TREC trial are published. The first results presented at ESTRO 2025 indicate that 57% of patients that received CRT maintained a clinical complete response one year after treatment compared to 27.3% in the arm with 5 \times 5 Gy (<https://user-swndwmf.cld.bz/ESTRO-2025-Abstract-Book>). The dosage of Capecitabine at 825mg/m² for five days per week has been chosen to mimic the STAR-TREC study.

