4.0 TRIAL OBJECTIVES

Investigate if using chemoradiotherapy 2 Gy x 25 with Capecitabine 825 mg/m² and a limited clinical target volume (CTV) will obtain a clinical complete response rate of 50% or more in patients with TX/T1-3b, NX/N0, MX/M0 rectal tumours.

The aim is to provide a treatment option to surgery to patients with early rectal cancer that fulfil the inclusion criteria for the now closed STAR-TREC study. This will enable a safe implementation with a control of outcomes and treatment regimens.

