Patients who achieve cCR may progress directly to active surveillance and included in the Swedish Watch and Wait study (WoW, NCT03125343). Clinical and radiological follow-up at 3, 6, 9, 12, 15, 18, 21 and 24 months. First year registered in CRF in this study too, after that follow-up at 1, 2 and 3 years.

Those who do not fulfil the criteria for cCR will progress to TME-surgery. Follow-up at 1, 2 and 3 years.

Time points for follow up and collection of data into CRF

1. Inclusion
2. Start of neoadjuvant treatment
3. Evaluation after neoadjuvant treatment
4. Second follow-up after neoadjuvant treatment if applicable
5. Third follow-up after neoadjuvant treatment if applicable
6. Surgery if applicable
7. Postoperative hospitalization if applicable
8. 1 month follow-up after surgery
9. 1 year after diagnosis
10. 2 years after diagnosis
11. 3 years after diagnosis
12. 5 years only through SCRCR and Swedish Cause of Death Registry

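### Hospital stay is summarised by median and range over 365 days: the CRT median is likely to be zero if few unoperated patients are admitted, and stays for later regrowth surgery are not counted

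*Protocol*

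**What the plan says.** Section 8.1.2 of the protocol defines the variable for total hospital stay as "Total number of days including readmissions", the summary as "Median and range" and the time point as "Within 365 days after diagnosis". The synopsis lists the same endpoint as "Total length of hospital stay during the first year", without a starting date. The row does not mention a comparison between groups, although the rows for urinary, sexual and bowel function do.

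Four other parts of the protocol bear on how this summary will behave:

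- Section 2.4 reports from the preceding trial that "57% of patients that received CRT maintained a clinical complete response one year after treatment". Section 4.0 asks whether the regimen "will obtain a clinical complete response rate of 50% or more in" the target population.
- Section 5.1 states: "Those who do not fulfil the criteria for cCR will progress to TME-surgery". Section 2.4 names patients who choose upfront TME as the control arm.
- Section 2.3 notes, from a cited randomised trial of radiotherapy boosts, that "some patients had their local regrowth after 3 years, indicating that long-term follow-up may be necessary". Section 8.1.2 records regrowth at one, two and three years, and section 5.4.3 ends the trial after three years of follow-up.
- Section 8.1.2 plans a health-economic analysis at three years that includes health-care costs.

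**The concern.** The CRT group is expected to be a mixture. One part is never operated on and, as capecitabine is taken as tablets and radiotherapy is given in daily fractions, may have no inpatient day at all. The other part goes on to TME and is admitted. When the first part, less anyone admitted for another reason, exceeds half of the group, the median is 0 whatever happens to the rest. A doubling of stay among the operated patients would not move it.

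That stay is of interest. Section 3.2 warns that patients who still need surgery may be over-treated and may have more postoperative complications, and section 2.3 says the treatment raises that risk. Days in hospital are one place where this would show.

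The window adds a second problem. Upfront TME falls inside 365 days of diagnosis, with time left for readmissions. Surgery for regrowth can fall after day 365 and is then not counted, although the trial follows these patients for three years.

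**Working it through.** **The plan's own figure.** The protocol gives no expected value for hospital stay, so there is none to reproduce. The only design figure used here is N = 82 from section 10.1. Its rule (49 or more responses) reproduces as one-sided: P(X ≥ 49 | 82, 0.50) = 0.0485. That result has no bearing on this point.

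**Inputs.**
- N = 82 (section 10.1); N = 60 and 80 as checks (synopsis estimate).
- c, the share of CRT patients not operated on within the window: 0.57 from section 2.4, with 0.60 (the synopsis says almost 60%) and 0.50 (the target in section 4.0) alongside. This treats complete response at one year as equal to not being operated on in the window, which is an approximation.
- h, the share of unoperated patients with any other admission in the window. The protocol gives no rate, so 0, 5, 10 and 20% are assumed.

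**Condition for a zero median.** Patients with no inpatient day make up c(1 − h) of the group. The expected median is 0 only if c(1 − h) > 0.5, that is h < (c − 0.5)/c:
- c = 0.57: 0.07/0.57 = 12.3%
- c = 0.60: 0.10/0.60 = 16.7%
- c = 0.50: no slack

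**Probability in the sample.** With 82 patients the median is the average of the 41st and 42nd ordered values, so it is 0 only if at least 42 patients have zero days. P(median = 0) = P(Binomial(82, c(1 − h)) ≥ 42):

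| c | h = 0 | h = 5% | h = 10% | h = 20% |
|---|---|---|---|---|
| 0.57 | 0.88 | 0.74 | 0.55 | 0.18 |
| 0.60 | 0.96 | 0.88 | 0.73 | 0.32 |
| 0.50 | 0.46 | 0.29 | 0.15 | 0.03 |

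At c = 0.57 and h = 0 the value is 0.83 for N = 60 and 0.875 for N = 80. If the trial just meets its success rule and all 49 responders are unoperated, the median is 0 unless at least 8 of them are admitted for another reason (49 − 7 = 42 zeros suffice; 49 − 8 = 41 do not).

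**What a zero median would hide.** Assume no other admissions and 43% operated. If operated patients stay 8 days on average, the group mean is 0.43 × 8 = 3.4 days per patient. If they stay 16 days it is 0.43 × 16 = 6.9. With more than half of the group at zero days, the median is 0 in both cases. The 8 and 16 days are illustrative.

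**What the window leaves out.** Timing follows from sections 5.1 and 7.3.9:
- Primary non-response: 5 weeks of CRT plus 12 weeks to the second evaluation is 17 weeks from the start of CRT. The resulting surgery normally falls inside 365 days.
- Regrowth: first assessment comes 5 + 6 to 5 + 8 = 11 to 13 weeks from the start of CRT. The nine-month visit after complete response (about 39 weeks) is then at about 50 to 52 weeks. Adding the interval from diagnosis to CRT and the wait for an operation, surgery for regrowth found at that visit or later would generally fall outside.

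If g is the share of one-year responders operated on after day 365, the window captures (1 − c)/(1 − c + cg) of the CRT group's surgical days, with equal stay per operation. At c = 0.57, assumed g of 5, 10 and 20% gives 94, 88 and 79%. The protocol gives no value for g.

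**The case against.** The strongest reply is that the endpoint is descriptive, has no stated group test, and reports the range beside the median. A zero median would also truthfully describe the typical CRT patient. All of this stands. The range, however, reports the extreme patients and not how many were admitted or how many days the group used, which is what a reader will look for in an endpoint on total stay.

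Several stronger readings might be inferred, and the protocol does not support them:

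- *The median is zero whenever most patients avoid surgery.* Any admission counts, and section 3.2 lists toxicities that could lead to one. The condition is that most patients have no admission at all. At 57% unoperated it fails in expectation once more than 12.3% of the unoperated are admitted. At 50% unoperated the probability of a zero median is only 0.46 even with no other admissions.
- *The measure favours CRT by construction.* This row specifies no group comparison, and surgery for primary non-response normally falls inside the window.
- *The 39% five-year regrowth in section 2.3 shows how much surgery is lost.* It comes from a trial with a radiotherapy boost that also admitted minor nodal disease, and no split at one year is given.
- *The Comprehensive Complications Index has the same fault.* It runs for 90 days from surgery and has no 365-day cut-off.

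The three-year health-economic analysis covers later costs in part, but its row specifies no summary of hospital days.

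**Conclusion.** The point holds in a limited form. The protocol itself fixes a summary that, in the scenario the trial hopes for, is likely to be 0 for CRT and unresponsive to the stay of the roughly 43% who are operated on. The probability at N = 82 is 0.88 with no other admissions and falls to 0.74, 0.55 and 0.18 as the assumed admission rate among unoperated patients rises to 5, 10 and 20%. It rests on taking the 57% response rate as the unoperated share and on those assumed rates.

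The omission of regrowth surgery after day 365 follows from the definition and falls mainly on the CRT group, but the protocol does not allow its size to be derived. This is a weakness in one descriptive secondary endpoint. It does not touch the primary analysis.

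**What to change.** Keep the one-year median and range. Add, by initial treatment choice, the mean number of inpatient days per patient with a bootstrap 95% CI and the proportion of patients with any admission. State the starting date in the synopsis so that it matches section 8.1.2.

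For CRT patients, also report inpatient days to three years, using the hospital-use data that the three-year health-economic analysis will need. Report the same for the TME group only if the national registry or that analysis supplies it. Sections 5.1 and 6.3 take that group's non-QoL data from the registry, and the protocol does not say that it holds three-year inpatient days. Without those data, present the three-year CRT figure alone and do not set it beside a one-year TME figure.

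The cost is slightly more analysis and a three-year figure that arrives later. Sample size, eligibility and treatment are unaffected, and no change to the Comprehensive Complications Index is needed.
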